- Alternative causes, such as underlying disease(s), concomitant therapy, and other risk factors, as well as the temporal relationship of the event to study intervention administration will be considered and investigated.
- The investigator will also consult the Investigator's Brochure (IB) and/or Product Information, for marketed products, in his/her assessment.
- For each AE/SAE, the investigator must document in the medical notes that he/she has reviewed the AE/SAE and has provided an assessment of causality.
- There may be situations in which an SAE has occurred and the investigator has minimal information to include in the initial report to Sponsor. However, it is very important that the investigator always make an assessment of causality for every event before the initial transmission of the SAE data to Sponsor.
- The investigator may change his/her opinion of causality in light of follow-up information and send a SAE follow-up report with the updated causality assessment.
- The causality assessment is one of the criteria used when determining regulatory reporting requirements.

Follow-up of AEs and SAEs

If only limited information is initially available, follow-up reports are required. (Note: Follow-up SAE reports must include the same investigator term(s) initially reported.)

If an ongoing SAE changes in its intensity or relationship to study treatment or if new information becomes available, the SAE report must be updated and submitted within 24 hours to BMS (or designee) using the same procedure used for transmitting the initial SAE report.

All SAEs must be followed to resolution or stabilization.

REPORTING OF SAES TO SPONSOR OR DESIGNEE

- SAEs, whether related or not related to study treatment, and pregnancies must be reported to BMS (or designee) immediately within 24 hours of awareness of the event.
- SAEs must be recorded on the SAE Report Form.
 - The required method for SAE data reporting is through the eCRF.
 - The paper SAE Report Form is only intended as a back-up option when the electronic data capture (EDC) system is unavailable/not functioning for transmission of the eCRF to BMS (or designee).
 - ♦ In this case, the paper form is transmitted via email or confirmed facsimile (fax) transmission
 - When paper forms are used, the original paper forms are to remain on site
- Pregnancies must be recorded on a paper Pregnancy Surveillance Form and transmitted via email or confirmed facsimile (fax) transmission

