	To explore the associations between PK of BMS-986249 and nivolumab, safety, efficacy, and clinical biomarkers such as, but not limited to T cell-specific genes	Association measures between BMS-986249 and nivolumab PK levels, select outcomes, and biomarkers of interest	
	• To characterize the immunogenicity of BMS-986249 and nivolumab	Incidence of ADA to nivolumab and BMS-986249	
	• To explore OS	OS rate at 1 and 2 years	
	To evaluate changes in QoL, health status, and patient reported tolerability	Mean scores and post-baseline score changes for all EORTC QLQ-C30 subscales, EQ-5D-3L utility index and VAS, and n (%) of endorsing participants by arm and time point for FACIT GP5 item and PRO-CTCAE items	

Abbreviations: ADA = anti-drug antibody; AE = adverse event; CRPC = castration-resistant prostate cancer; DOR = duration of response; EQ-5D-3L = European Quality of Life – 5 Dimension – 3 Level Questionnaire; EORTC QLQ-C30 = European Organisation for Research and Treatment of Cancer Quality of Life Questionnaire – Core 30; FACIT GP5 = functional assessment of chronic illness therapy general physical item 5; HCC = hepatocellular carcinoma; ORR = objective response rate; OS = overall survival; PCWG3 = Prostate Cancer Working Group 3; PFS = progression-free survival; PK = pharmacokinetics; PRO-CTCAE = patient reported outcomes version for Common Terminology Criteria for Adverse Events; PSA = prostate-specific antigen; QoL = quality of life; RECIST = Response Evaluation Criteria in Solid Tumors; SAE = serious adverse events; TNBC = triple-negative breast cancer; TTR = time to response; VAS = visual analogue scale.

Table 4-4: Primary Estimands Part 2A

Objectives	Endpoints
Primary	Primary
To evaluate the preliminary safety and tolerability of BMS-986249 in combination with nivolumab (Arm C and Arm F) relative to ipilimumab in combination with nivolumab (Arm D) in participants with previously untreated, unresectable or metastatic melanoma	Incidence of treatment-related Grade 3-5 AEs within 24 weeks

Protocol Amendment No.: 09

Table 4-4: Primary Estimands Part 2A

Main Estimand for the Primary Objective

Treatment: 1200 mg BMS-986249 IV Q8W + 480 mg nivolumab IV Q4W (Arm C); 3 mg/kg ipilimumab Q3W + 1 mg/kg nivolumab IV Q3W for 4 doses followed three weeks later by 480 mg nivolumab IV Q4W(Arm D); 600 mg BMS-986249 IV Q4W +480 mg nivolumab IV Q4W (Arm F)

Population: All treated participants

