Variable: Treatment Related AE with CTCAE Grade 3 or higher that occurred within 24 weeks from first dose Intercurrent events: early discontinuation of study

Treatment Policy: Patients that discontinue treatment early will have a 100 days post last dose safety follow-up. AEs occurring after this safety follow-up window will not be included in the analysis, even if they occurred within the 24 weeks from first dose.

Intercurrent event: initiation of subsequent anti-cancer therapy

While on treatment: Patients that initiate an anti-cancer subsequent therapy will be discontinued from study but will be followed up for safety events 100 days from last dose. Safety events regardless of whether they occur before or after subsequent therapy will be include in the analysis. AEs occurring past 100 days safety follow-up will not be included in the analysis, even if they occurred within the 24 weeks from first dose.

Intercurrent event: death and withdrew

While on treatment: Patients who die or withdraw consent before reaching the 24 weeks landmark will be included in the analysis and their Grade 3 to 5 treatment related AEs will be include in the summary.

Population level summary: Grade 3 to 5 treatment related adverse event incidence rate, comparison of Arm C vs Arm D and Arm F vs Arm D with estimated difference and odd ratio and 80% confidence interval using Cochran Mantel Haenszel methodology adjusting for stratification factors will be computed. Adjusted and unadjusted chi square test will be performed and p-values will be provided.

Objective	Endpoint
Primary	Primary
To evaluate the preliminary efficacy of BMS-986249 in combination with nivolumab (Arm C and Arm F) relative to historic nivolumab monotherapy data in participants with previously untreated, unresectable or metastatic melanoma	ORR as assessed by investigator using RECIST v1.1

Main Estimand for the Primary Objective

Treatment: 1200 mg BMS-986249 IV Q8W + 480 mg nivolumab IV Q4W (Arm C); 3 mg/kg ipilimumab Q3W + 1 mg/kg nivolumab IV Q3W for 4 doses followed three weeks later by 480 mg nivolumab IV Q4W(Arm D); 600 mg BMS-986249 IV Q4W + 480 mg nivolumab IV Q4W (Arm F)

Population: All treated participants with evaluable baseline tumor assessment per RECIST v1.1

Variable: BOR, defined as the best response, as determined by investigator, per RECIST 1.1

Intercurrent events: early discontinuation of study

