5.5.1.3 Starting Dose Selection Based on Ipilimumab Clinical Safety Data⁵¹

The AEs of ipilimumab in cancer patients are mostly irAEs, which have been well defined in terms of their incidence, severity, time to onset, and resolution. In participants with advanced melanoma, the irAEs of ipilimumab at 3 mg/kg Q3W for 4 cycles occurred in approximately 60% to 65% of the participants. These AEs were mostly Grade 1-2 and affected primarily the skin (in 43% to 45% of participants) and GI tract (in 29% to 32% of participants), followed by the liver and endocrine system (in 6% to 8% of participants). The vast majority of these irAEs occurred within 12 weeks of initial dosing, with a median time of Grade 2-4 irAEs occurring at 4.6 weeks. ⁵² In addition, low incidence of infusion-related reaction (IRR) of ipilimumab was also reported in 2.2% and 4.3% of participants treated at 3 and 10 mg/kg infused over 90 minutes and can be treated with premedication of diphenhydramine. ⁵⁶ Management of irAEs attributed to ipilimumab treatment have been well established in the REMS Guidelines approved by FDA. ⁵³

BMS-986249 is expected to have the same type but reduced irAEs compared with ipilimumab based on the Probody mAb mechanism, which has been demonstrated in the nonclinical pharmacology and GLP toxicology studies. The efficacious dose of BMS-986249 is projected to be 3 mg/kg, same as the ipilimumab approved clinical dose. Therefore, an FIH starting dose of BMS-986249 at 240 mg (equivalent to approximately 3 mg/kg) may achieve anti-tumor efficacy similar to that of ipilimumab and reduced toxicities in participants that can be well managed based on ipilimumab REMS guidelines.

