7.4 Blinding

This is an open-label study and randomized in Part 2A. Designated staff of the Sponsor may receive access to treatment codes prior to database lock to facilitate early exploratory data analysis and the bioanalytical analysis of PK samples and immunogenicity. A bioanalytical scientist in the Sponsor's Bioanalytical Sciences department (or a designee in the external central bioanalytical laboratory) will have access to the randomized treatment assignments in order to minimize unnecessary bioanalytical analysis of samples. In addition, the Sponsor's Research and Development team will have access to the treatment codes prior to final data base lock for ongoing evaluation of preliminary available data (eg, safety, PK, and

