 - Dosing delays lasting > 8 weeks from the previous dose that occur for non-drug-related reasons may be allowed if approved by the Medical Monitor (or designee).
- For Part 2A Arms A and D during the Combination Therapy Phase, decisions to discontinue study treatment therapy must include both nivolumab as well as BMS-986249 or ipilimumab. It is not permitted to continue nivolumab without BMS-986249 or ipilimumab. Part 2A Arm A and D participants who do not complete all scheduled cycles of BMS-986249 or ipilimumab and nivolumab combination therapy will not be eligible for the nivolumab monotherapy Maintenance Phase.
- For Part 1B, Part 2A Arms B, C, and F, and Part 2B, the assessment for discontinuation of nivolumab should be made separately from the assessment made for discontinuation of BMS-986249, if possible. Although there is overlap among the discontinuation criteria, if discontinuation criteria are met only for BMS-986249 but not for nivolumab, treatment with nivolumab may continue after discussion and approval by the Medical Monitor (or designee). Treatment with BMS-986249 may continue if nivolumab is discontinued only if the investigator is able to clearly determine the discontinuation event is only related to nivolumab treatment and the decision is discussed with and approved by the Medical Monitor (or designee).

BMS-986249, as a Probody of ipilimumab, is predicted to have a similar but attenuated irAE profile compared to ipilimumab. The activation of a pre-existing but attenuated immune response

to cancer by checkpoint blockade is associated with an AE profile that is inherent to immune activation. Hence, distinguishing between an ipilimumab and nivolumab AE can be difficult. Clinical trial experience and labeled indications have characterized the AE profiles of ipilimumab and nivolumab and suggest that some events are more frequently associated with a specific agent (eg, pneumonitis is more common with nivolumab than ipilimumab). Listed below are the most common irAE and AEs of ipilimumab and nivolumab. Refer to section 7.5.1 for information on DLTs.

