- elective surgery, planned prior to signing consent
- admissions as per protocol for a planned medical/surgical procedure
- routine health assessment requiring admission for baseline/trending of health status (e.g., routine colonoscopy)
- medical/surgical admission other than to remedy ill health and planned prior to entry into the study. Appropriate documentation is required in these cases
- admission encountered for another life circumstance that carries no bearing on health status and requires no medical/surgical intervention (e.g., lack of housing, economic inadequacy, caregiver respite, family circumstances, administrative reason)
- admission for administration of anticancer therapy in the absence of any other SAEs (applies to oncology protocols)

Results in persistent or significant disability/incapacity

Is a congenital anomaly/birth defect

Protocol Amendment No.: 09

Is an important medical event (defined as a medical event(s) that may not be immediately life-threatening or result in death or hospitalization but, based upon appropriate medical and scientific judgment, may jeopardize the participant or may require intervention [e.g., medical, surgical] to prevent one of the other serious outcomes listed in the definition above.) Examples of such events include, but are not limited to, intensive treatment in an emergency room or at home for allergic bronchospasm; blood dyscrasias or convulsions that do not result in hospitalization.) Potential drug induced liver injury (DILI) is also considered an important medical event. (See Section 9.2.8 for the definition of potential DILI.)

Pregnancy and potential drug induced liver injury (DILI) must follow the same transmission timing and processes to BMS as used for SAEs (see section 9.2.5 for reporting pregnancies).

Any component of a study endpoint that is considered related to study therapy should be reported as SAE (e.g., death is an endpoint, if death occurred due to anaphylaxis, anaphylaxis must be reported).

EVALUATING AES AND SAES

Assessment of Causality

- The investigator is obligated to assess the relationship between study intervention and each occurrence of each AE/SAE.
- A "reasonable possibility" of a relationship conveys that there are facts, evidence, and/or arguments to suggest a causal relationship, rather than a relationship cannot be ruled out.
- The investigator will use clinical judgment to determine the relationship.

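### The open-label primary safety contrasts in Part 2A count only events the investigator calls treatment-related, and the protocol specifies no same-window all-causality contrast to check them against

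*Combined protocol and SAP*

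**What the plan says.** Table 4-4 defines the Part 2A primary safety estimand in all treated participants: "Variable: Treatment Related AE with CTCAE Grade 3 or higher that occurred within 24 weeks from first dose". The population-level summary is a "comparison of Arm C vs Arm D and Arm F vs Arm D with estimated difference and odd ratio and 80% confidence interval", by Cochran-Mantel-Haenszel (CMH) methods on the stratification factors, with adjusted and unadjusted chi-square p-values.

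Section 7.4 states: "This is an open-label study and randomized in Part 2A". Appendix 3 (Assessment of Causality) leaves relatedness to the investigator: "The investigator will use clinical judgment to determine the relationship". It adds: "The investigator will also consult the Investigator's Brochure (IB) and/or Product Information, for marketed products, in his/her assessment". No blinded or independent review of relatedness is described.

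The protocol also states what it expects of the new drug. Section 8.1: "BMS-986249, as a Probody of ipilimumab, is predicted to have a similar but attenuated irAE profile compared to ipilimumab". Section 5.5.1.3: "BMS-986249 is expected to have the same type but reduced irAEs compared with ipilimumab".

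All-causality events are collected (Section 9.2.1) and are a secondary endpoint for Arms C, D and F (Table 4-2), with no 24-week limit in the endpoint. In Table 10.3.2-1 their method is a frequency distribution by worst grade. Only the row for treatment-related Grade 3-5 events carries a ratio, a difference and confidence intervals. Section 10.3 calls itself a summary and defers to a statistical analysis plan to be finalized before database lock. That plan is not part of the document reviewed.

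**The concern.** Whether a participant counts as a case depends on a judgment made with the arm known and a milder profile predicted for one arm. Appendix 3 leaves room for discretion. A relationship must be supported by facts or argument, not merely be impossible to exclude, and underlying disease and concomitant therapy must be weighed as alternative causes.

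If that threshold were applied differently in Arms C and F than in Arm D, the related-event rates would differ even with the same true toxicity. A contrast of all Grade 3-5 events over the same 24 weeks does not depend on relatedness labels, so it would be the direct check. The protocol does not specify one. At stake is how a reader should interpret a favourable tolerability result, which is one of the two primary findings of Part 2A.

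**Working it through.** **Inputs from the documents.** 60 participants per arm, two-group chi-square, one-sided alpha 0.10, about 70% power (Section 10.1.2.2). The control-arm rate and the target ratio are blacked out.

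**Assumed.** True related Grade 3-5 rate 40-55%, equal in both arms. The only visible melanoma figure for the control regimen is 55.0% (Grade 3-4, not limited to 24 weeks; Table 5.4.7.1-1), used here as the upper end. A share *m* of cases is relabelled as unrelated in the experimental arm only.

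**Formula.** With control rate pC, experimental rate pE, mean rate p̄ and n per arm:

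P(reject) = Φ{[(pC − pE) − 1.2816·√(2p̄(1−p̄)/n)] / √[(pC(1−pC) + pE(1−pE))/n]}

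**The plan's own figure.** The 70% cannot be confirmed, because both rates are hidden. It is plausible: 60 per arm gives 70% for 40% vs 24.6%, 45% vs 29.1%, 50% vs 33.8% or 55% vs 38.6%, which are relative reductions of 30-38%.

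**Effect of one-sided relabelling.** Set pE = pC(1 − m). For pC = 50% and m = 10%, pE = 45% and p̄ = 47.5%. The two standard errors are √(2 × 0.475 × 0.525/60) = 0.0912 and √((0.25 + 0.2475)/60) = 0.0911. Then Φ{(0.05 − 1.2816 × 0.0912)/0.0911} = Φ(−0.73) = 0.23.

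| Assumed rate | m = 0 | m = 10% | m = 20% | m = 30% |
|---|---|---|---|---|
| 40% | 0.10 | 0.20 | 0.36 | 0.54 |
| 45% | 0.10 | 0.22 | 0.39 | 0.60 |
| 50% | 0.10 | 0.23 | 0.43 | 0.65 |
| 55% | 0.10 | 0.25 | 0.47 | 0.70 |

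Exact binomial enumeration gives 0.22-0.25 at m = 10% and 0.10-0.11 at m = 0.

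**Events versus participants.** The endpoint is counted per participant, so a case is lost only if every qualifying event is relabelled. Take a 50% rate, 10% of events relabelled independently, and SE = √(2 × 0.25/60) = 0.0913:
- Half the cases have two events: the share lost is 0.5 × 0.10 + 0.5 × 0.01 = 0.055. The shift is 0.50 × 0.055 = 2.75 points, and rejection is 1 − Φ(1.2816 − 0.0275/0.0913) = 0.16.
- All cases have two events: the share lost is 0.01. The shift is 0.5 points, and rejection is 1 − Φ(1.2816 − 0.005/0.0913) = 0.11.

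The 23% therefore corresponds to one qualifying event per case, or to relabelling that goes together within a participant.

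**Power of the supportive contrast.** Add an unrelated Grade 3-5 rate *b*, equal in both arms, so that the all-causality rate is 1 − (1 − r)(1 − b), where r is the related rate. Starting from the 70% design points, power is about 61-63% for b = 10%, 53-57% for b = 20% and 46-51% for b = 30%. With equal true toxicity, relabelling leaves its rejection rate at 10%.

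**The case against.** The strongest reply concerns the mechanism. The endpoint asks whether an event is related to study treatment, and in Arms C and F that includes nivolumab. An event blamed on nivolumab still counts, so bias needs an event called unrelated to both drugs. The Section 8.1 sentence sits in text about stopping one drug or both, not about related versus unrelated, and that section lists largely overlapping immune-related events for ipilimumab and nivolumab. This stands. It narrows the route to bias without closing it, because disease and concomitant therapy remain available as alternative causes.

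The expectation is also not one-sided. Section 3.2.1.6 calls the observed profile consistent with ipilimumab and notes a possible increased encephalitis risk. Expecting the same types of event may encourage attribution to treatment. A reader might infer that the primary comparison is biased in favour of BMS-986249; the documents do not establish that.

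A reader might also infer that the planned outputs cannot distinguish relabelling from a real reduction. That goes too far. All-causality worst-grade tables, discontinuations, deaths and laboratory shift tables are planned, as are PRO-CTCAE and FACIT GP5 by arm and time point. None depends on relatedness labels, and together they give a partial check. Nor does the protocol say that the all-causality tables cover the whole reporting period. It gives them no window; Section 9.2.1 is a collection rule.

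Finally, related events match the benchmark used for sizing, and Section 10.1.2.2 describes an exploratory proof-of-concept design. Both are good reasons to keep the primary endpoint, but neither argues against a supportive table.

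**Conclusion.** The point holds as a gap in the specified analyses, not as a demonstrated bias. Between-arm estimates with intervals are specified for the investigator-attributed endpoint alone. The all-causality counterpart over the same 24 weeks has none in the protocol, so the primary result lacks a direct check against differential attribution. Whether the separate analysis plan adds one cannot be judged here.

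The possible size is illustrative. With 10% of cases relabelled in the experimental arm only, a single comparison rejects about 20-25% of the time instead of 10%, for assumed rates of 40-55%. With two events per participant in half or all cases, relabelled independently, it rejects about 11-16%. Every rate and relabelling share is an assumption. This is a low-cost improvement and does not invalidate the primary analysis.

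**What to change.** In Table 4-4 and Section 10.3.2, prespecify all-causality Grade 3-5 adverse events within 24 weeks of first dose, for C vs D and F vs D, as a supportive analysis. Use the same treated population, the same window (including the 100-day limit after last dose), the same CMH strata and the 80% confidence interval, and report it beside the primary result. It should carry no formal decision gate: the primary endpoint and its interpretation rule stay as they are.

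The cost is one more table from adverse-event data the protocol already collects. One collection detail should be settled at the same time. A bullet in Section 9.2.1 exempts participants who have started new anti-neoplastic therapy from routine collection, while Table 4-4 counts events before and after subsequent therapy.

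The analysis has two limits. Disease-related events dilute the contrast, which is why it suits a supportive role and should not replace the primary. It also does nothing about open-label bias in grading or in reporting events at all.

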APPENDIX 4 WOMEN OF CHILDBEARING POTENTIAL DEFINITIONS AND METHODS OF CONTRACEPTION

DEFINITIONS

Woman of Childbearing Potential (WOCBP)

A woman is considered fertile following menarche and until becoming post-menopausal unless permanently sterile. Permanent sterilization methods include hysterectomy, bilateral salpingectomy, and bilateral oophorectomy.

Women in the following categories are not considered WOCBP

- Premenarchal
- Premenopausal female with 1 of the following:
 - Documented hysterectomy
 - Documented bilateral salpingectomy
 - Documented bilateral oophorectomy

Note: Documentation can come from the site personnel's review of the participant's medical records, medical examination, or medical history interview.

- Postmenopausal female
 - A postmenopausal state is defined as 12 months of amenorrhea in a woman over age 45 years in the absence of other biological or physiological causes. In addition, females under the age of 55 years must have a serum follicle stimulating hormone (FSH) level > 40 mIU/mL to confirm menopause.

Note: Females treated with hormone replacement therapy (HRT) are likely to have artificially suppressed FSH levels and may require a washout period in order to obtain a physiologic FSH level. The duration of the washout period is a function of the type of HRT used. The duration of the washout period below are suggested guidelines and the investigators should use their judgement in checking serum FSH levels.

- 1 week minimum for vaginal hormonal products (rings, creams, gels)
- 4 week minimum for transdermal products
- 8 week minimum for oral products

Other parenteral products may require washout periods as long as 6 months. If the serum FSH level is > 40 mIU/ml at any time during the washout period, the woman can be considered postmenopausal.

Protocol Amendment No.: 09

CONTRACEPTION GUIDANCE FOR FEMALE PARTICIPANTS OF CHILD BEARING POTENTIAL

One of the highly effective methods of contraception listed below is required during study duration and until the end of relevant systemic exposure. For combination therapy with BMS-986249 plus nivolumab, relevant systemic exposure is defined as 125 days after the end of study treatment, plus 30 days, for a total of 155 days post treatment completion. For monotherapy with BMS-986249, relevant systemic exposure is defined as 75 days after the end of study treatment, plus 30 days, for a total of 105 days post treatment completion. For ipilimumab in combination with nivolumab therapy, the end of relevant systemic exposure is defined as 5 months after the end of study treatment. For monotherapy with nivolumab, the end of relevant systemic exposure is defined as 5 months after the end of study treatment.

Local laws and regulations may require use of alternative and/or additional contraception methods.

Highly Effective Contraceptive Methods That Are User Dependent

Failure rate of <1% per year when used consistently and correctly.^a

- Combined (estrogen- and progestogen-containing) hormonal contraception associated with inhibition of ovulation and/or implantation (These methods of contraception cannot be used by WOCBP participants in studies where hormonal contraception is prohibited)^b
 - Oral (birth control pills)
 - Intravaginal (vaginal birth control suppositories, rings, creams, gels)
 - Transdermal
- Progestogen-only hormonal contraception associated with inhibition of ovulation^b
 - Oral
 - Injectable

Highly Effective Methods That Are User Independent

- Implantable progestogen-only hormonal contraception associated with inhibition of ovulation and/or implantation (This method of contraception cannot be used by WOCBP participants in studies where hormonal contraception is prohibited)^b
- Intrauterine device (IUD)^c
- Intrauterine hormone-releasing system (IUS) (This method of contraception cannot be used by WOCBP participants in studies where hormonal contraception is prohibited)^{b c}
- Bilateral tubal occlusion
- Vasectomized partner

A vasectomized partner is a highly effective contraception method provided that the partner is the sole male sexual partner of the WOCBP and the absence of sperm has been confirmed. If not, an additional highly effective method of contraception should be used.

Sexual abstinence

Sexual abstinence is considered a highly effective method only if defined as refraining from heterosexual intercourse during the entire period of risk associated with the study treatment. The reliability of sexual abstinence needs to be evaluated in relation to the duration of the study and the preferred and usual lifestyle of the participant.

- It is not necessary to use any other method of contraception when complete abstinence is elected.
- WOCBP participants who choose complete abstinence must continue to have pregnancy tests, as specified in Section 2.
- Acceptable alternate methods of highly effective contraception must be discussed in the event that the WOCBP participants choose to forego complete abstinence

NOTES:

- Typical use failure rates may differ from those when used consistently and correctly. Use should be consistent with local regulations regarding the use of contraceptive methods for participants participating in clinical studies.
- b Hormonal contraception may be susceptible to interaction with the study treatment, which may reduce the efficacy of the contraceptive method. Hormonal contraception is permissible only when there is sufficient evidence that the investigational medicinal product (IMP) and other study medications will not alter hormonal exposures such that contraception would be ineffective or result in increased exposures that could be potentially hazardous. In this case, alternative methods of contraception should be utilized.
- ^c Intrauterine devices and intrauterine hormone releasing systems are acceptable methods of contraception in the absence of definitive drug interaction studies when hormone exposures from intrauterine devices do not alter contraception effectiveness

Less Than Highly Effective Contraceptive Methods That Are User Dependent

Failure rate of >1% *per year when used consistently and correctly.*

- Male or female condom with or without spermicide. Male and female condoms cannot be used simultaneously
- Diaphragm with spermicide
- Cervical cap with spermicide
- Vaginal sponge with spermicide
- Progestogen-only oral hormonal contraception, where inhibition of ovulation is not the primary mechanism of action (This method of contraception cannot be used by WOCBP participants in studies where hormonal contraception is prohibited)

Unacceptable Methods of Contraception

- Periodic abstinence (calendar, symptothermal, post-ovulation methods)
- Withdrawal (coitus interruptus).
- Spermicide only
- Lactation amenorrhea method (LAM)

Protocol Amendment No.: 09

CONTRACEPTION GUIDANCE FOR MALE PARTICIPANTS WITH PARTNER(S) OF CHILD BEARING POTENTIAL.

Male participants with female partners of childbearing potential are eligible to participate if they agree to the following during the treatment and until the end of relevant systemic exposure.

- Inform any and all partner(s) of their participation in a clinical drug study and the need to comply with contraception instructions as directed by the investigator.
- Male participants are required to use a condom for study duration and until the end of relevant systemic exposure, defined as 165 days after the end of BMS-986249 monotherapy treatment, 215 days after the end of BMS-986249 + nivolumab combination therapy treatment, 7 months after the end of ipilimumab + nivolumab combination therapy treatment, and 7 months after the end of nivolumab monotherapy treatment in the male participant.
- Female partners of males participating in the study to consider use of effective methods of contraception until the end of relevant systemic exposure, defined as during the study treatment and until 165 days after the end of BMS-986249 monotherapy treatment, 215 days after the end of BMS-986249 + nivolumab combination therapy treatment, 7 months after the end of ipilimumab + nivolumab combination therapy treatment, and 7 months after the end of nivolumab monotherapy treatment in the male participant.
- Male participants with a pregnant or breastfeeding partner must agree to remain abstinent from penile-vaginal intercourse or use a male condom during each episode of penile penetration during the treatment and until 165 days after the end of BMS-986249 monotherapy treatment, 215 days after the end of BMS-986249 + nivolumab combination therapy treatment, 7 months after the end of ipilimumab + nivolumab combination therapy treatment, and 7 months after the end of nivolumab monotherapy treatment.
- Refrain from donating sperm for the duration of the study treatment and for 165 days after the end of BMS-986249 monotherapy treatment, 215 days after the end of BMS-986249 + nivolumab combination therapy treatment, 7 months after the end of ipilimumab + nivolumab combination therapy treatment, and 7 months after the end of nivolumab monotherapy treatment.

COLLECTION OF PREGNANCY INFORMATION

Guidance for collection of Pregnancy Information and outcome of pregnancy on the Pregnancy Surveillance Form is provided in Section 9.2.5 and the Appendix for Adverse Events and Serious Adverse Events Definitions and Procedures for Evaluating, Follow-up, and Reporting.

